**Specific Aim 1:** Conduct elicitation research with 20 Appalachian LGB emerging adults and LGB community leaders in order to develop effective intervention materials and stress targets. Participants will be asked to describe the type and frequency of sexual minority stressors faced by LGB emerging adults in their region (to create EW prompts and SA vignettes) and strategies to enhance the LGB-affirmative look-and-feel of the Phase 3 online platform.

**Specific Aim 2:** Present Specific Aim 1 results to 10 Appalachian LGB emerging adults and LGB community leaders to refine the EW prompts and SA vignettes and the LGB-affirmative, culturally relevant look-and-feel of the online platform. Identify, with these leaders, the most effective venues and materials for participant recruitment and retention, and identify the most effective modalities for future intervention dissemination.

**Specific Aim 3:** Pilot test feasibility and efficacy of writing interventions. 108 Appalachian LGB emerging adults will be randomized to complete one of three writing interventions (EW, SA, Control). They will be asked to complete outcome measures (depressive symptoms, suicidality, use of alcohol and illicit drugs, HIV risk behavior) and measures of proposed mediators (self-reported and biological stress, behavioral and emotional self-regulation) and moderators (e.g., social support,

identity centrality) at baseline, post-intervention, and three-month follow-up. In addition, structured interviews with 15 intervention participants will be used to refine study procedures as we scale up this intervention for a future RCT. Primary analyses will determine efficacy; secondary analyses will determine the moderating role of social support, gender, and other psychosocial factors (e.g., baseline risk) and estimate the effect sizes of the mediators of intervention efficacy for use in a subsequent RCT to determine the long-term efficacy and mechanisms of these interventions.

Despite evidence indicating that mental and physical health disparities are most severe among LGB emerging adults living in rural areas of the U.S., there are currently no evidence-based psychological interventions designed to mitigate sexual minority stress effects among this population (19). The proposed culturally-relevant, theory-based interventions are poised to reduce this gap and, therefore, address one of the most pressing public health goals of the U.S. Department of Health and Human Services (20, 21).

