#### PHASE/AIM 3:

We will recruit 108 Appalachian LGB emerging adults (36 per group) who (i) are aged 18-29, (ii) self-identify as a sexual minority (e.g., lesbian, gay, bisexual, pansexual, queer), (iii) currently live in Eastern Tennessee counties of Washington, Sullivan, Carter, Unicoi, Greene, or Hawkins County, and (iv) have daily personal internet access. Participants will be recruited, screened, and consented for an online writing intervention using Phase 1 strategies. Recruited individuals will be directed to complete a brief online screener gauging eligibility where they will consent to share their information with the research team. Those who consent to the online screener and meet the study eligibility criteria will then receive a call from a research team member who will share additional information about the study and gain consent for study participation. During the consent call, study staff will confirm participant age, contact information (such as phone number and address), and give participants the option to provide a secondary contact. After providing consent, participants will be emailed a link to complete an online baseline assessment (Study Task 1), then randomized to one of the three online writing interventions to be completed daily for three days starting the Monday of the following week (Study Task 2-Study Task 4). Participants will have up to two weeks to complete the three days of writing prompts. If the participant has not begun their first writing day (Study Task 2) within 24 hours of receiving the prompt than they will receive one email reminder per day for three days encouraging them to complete their writing prompt. If they still have not completed their writing prompt by the fifth day, then a research team member will try calling or texting the participant to remind them to complete the task. Upon completion of the first writing day (Study Task 2), the participant will have 24hrs to complete the second writing day (Study Task 3). If the participant does not complete the second writing day (Study Task 3) within 24 hours, then study staff will use the same email, text, and call reminder system as with writing day one (Study Task 2) to encourage them to complete writing day two (Study Task 3). The same communication and reminder protocol will be followed to encourage the participant to complete the third writing day (Study Task 4). Cumulatively, participants will have 14 days to complete the three writing prompts, but participants will not be invited to move on to the second writing prompt without first completing the prompt from writing day one, nor will they be prompted to complete the third writing task without submitting the second writing task. Seven days after completing their final writing task, or seven days after the close of the

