
two week writing window participants will be emailed a link to complete the post-intervention survey (Study Task 5). 30 days after completion of the first survey, and 30 days after completing the 3-month online follow-up assessment survey, participants will be mailed materials to collect a hair sample in order to assay for cortisol. At 3 months after completion of the post-intervention survey, participants will receive and complete a follow-up assessment via online survey. Lastly, we will randomly select 15 participants from Phase 3 for a follow up one-hour phone or internet-based interview where we will ask about participant experience with the writing sessions.

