#### **Control (C) Intervention:**

Participants randomly assigned to the control condition will be asked to write about what they have done since waking up that morning for 20 minutes across 3 Writing Days. This mundane control matches the time and activity of the EW and SA arms.

The online program that captures participants' writing will ensure that each participant writes for 20 minutes by not allowing the participant to advance until 20 minutes have passed. After each writing session, participants will be provided with the contact information of a local mental health resource center and a research assistant will review each submission within 24 hours to ensure each participant's safety. If participant expresses intentions of self-harm or harm towards others the research assistant will contact 911 in the Eastern Tennessee region. PI [name], a licensed clinical psychologist, will also contact participants who indicate threat to self or others or severe emotional distress.

Drs. [name] and [name] will train a graduate research assistants at ETSU to administer the consent process, tracking database, and online intervention systems. Phase 3 assessments

and interventions will be delivered via Qualtrics.com, for which Yale University has an ongoing subscription. Research assistants will be trained to check the account once per day to ensure the safety of participants by reviewing their writing and to send reminder emails, text messages, and calls to participants who skipped a day. Drs. [name] and [name] will perform biweekly review of all systems to verify RA protocol adherence.

4. **Participant Population:** Provide a detailed description of the types of participants who will be recruited into this study.

Participants in this study will be Appalachian sexual minority (LGBTQ+) emerging adults who (i) are aged 18-29, (ii) self-identify as LGBTQ+, and (iii) currently live in Eastern Tennessee counties of Washington, Sullivan, Carter, Unicoi, Greene, or Hawkins County. (Note: there is no age-restriction for the pre-identified community leaders/stakeholders in Phase 1 and Phase 2.)

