## **Mental Health and Risk**

Center for Epidemiological Studies -- Depression Scale (CESD), Brief Symptom Inventory (BSI), Beck Anxiety Inventory (BAI), Suicidality, Suicidal Ideation Attributes Scale (SIDAS), Self-Injury, Alcohol Use Disorders Identification (AUDIT), Short Inventory of Problems-Modified for Drug Use (SIP-DU), Sexual Behavior with Main Partner (SB-MP), Sexual Behavior with Casual Partners (SB-CP), Health Care Access and Experiences

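### The 24-hour safety review is written for the writing tasks only; no one is assigned to read the suicidality answers in the three online surveys

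*Protocol*

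**What the plan says.** The operational safety review is in the Protocol, Section IV, under the control arm description. After each writing session, "a research assistant will review each submission within 24 hours". The same text sets the consequence: "If participant expresses intentions of self-harm or harm towards others the research assistant will contact 911 in the Eastern Tennessee region". It adds that a licensed clinical psychologist will contact participants who indicate a threat or severe distress. The next paragraph says that Qualtrics delivers both the Phase 3 assessments and the interventions, and then describes the daily task: "Research assistants will be trained to check the account once per day to ensure the safety of participants by reviewing their writing".

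Suicidality is measured elsewhere. Specific Aim 3 says of participants: "They will be asked to complete outcome measures (depressive symptoms, suicidality, use of alcohol and illicit drugs, HIV risk behavior", with timing "at baseline, post-intervention, and three-month follow-up". The list of measures in Section VI, under Mental Health and Risk, names "Suicidality, Suicidal Ideation Attributes Scale (SIDAS), Self-Injury". The surveys are completed remotely. At the start, "participants will be emailed a link to complete an online baseline assessment (Study Task 1"; at 3 months, "participants will receive and complete a follow-up assessment via online survey". The post-intervention survey is also an emailed link, sent seven days after the last writing task or after the two-week writing window closes.

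Statements of wider scope appear in Section V item 10 (911 for imminent risk, judged by staff with mental health training), Section VI item 3 and Section VII (confidentiality is broken for clear intent to harm), Section VII (distress training and referral to free counseling) and Section VIII item 1 (a referral list). The Data and Safety Monitoring Plan has the principal investigator conduct safety reviews quarterly. The SAP analyses suicidality at both follow-ups and says nothing about safety contacts.

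**The concern.** The surveys put direct questions about suicidality and self-injury to every participant, in a population that the protocol's Background describes as at raised risk. The stated eligibility criteria do not exclude current suicidality, so the baseline survey may be the first place it is disclosed. Two of the three surveys come after the writing tasks, when no writing is left to review.

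A research assistant who followed the daily check exactly as written would read the free text and need not open the survey answers. The same disclosure would be read within 24 hours in a writing task but has no assigned reader in a survey. What is at stake is participant safety in a trial that asks about suicidality by design. There is also a point for interpretation. The expressive writing prompt asks for a most stressful event and the control prompt asks about the day's activities, so a review based on writing alone may find equally distressed participants at different rates by arm. The documents do not allow that difference to be quantified.

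**Working it through.** The plan gives no figure to reproduce. The check compares each provision on what is read, by whom, how soon, and what prompts action.

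| Provision | What is read | Reader | Time limit | Trigger |
|---|---|---|---|---|
| Review after writing (Section IV) | Writing submissions | Research assistant | 24 hours | Expressed intention, then 911 |
| Daily account check (Section IV) | Writing | Research assistant | Daily | Not separately stated |
| Psychologist contact (Section IV) | Not named | Not named | None | Threat or severe distress |
| 911 rule (Section V item 10) | Not named | Not named; trained staff judge | None | Imminent risk |
| Breach of confidentiality (Sections VI and VII) | Not named | Not named | None | Clear intent to harm |
| Distress training, referrals (Sections VII and VIII) | Not named | Staff in contact | None | Distress that staff are aware of |
| Biweekly systems review (Section IV) | Research assistant adherence | Investigators | Biweekly | Not applicable |
| Quarterly safety review (Section VII) | Study as a whole | Principal investigator | Quarterly | Continue, modify or close |

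Only the first two rows assign someone to read participants' responses for safety within a set time, and both are about writing. Rows three to six are not limited to writing, but each begins once a staff member knows of the disclosure. The last two concern conduct of the study, not individual answers.

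The survey dates do not bring them under the writing review. Baseline comes before randomization and the writing days. The post-intervention survey comes seven days after the final writing task or the close of the window. The last survey comes 3 months after that.

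Coverage, using 108 participants (Specific Aim 3), three writing tasks, three surveys, and the 83% to 100% retention that Section VIII reports from the investigators' previous studies:

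- Writing submissions with a stated 24-hour review, at full completion: 108 × 3 = 324.
- Surveys with no stated review, at full completion: 108 × 3 = 324.
- The same with 83% at both follow-ups: 108 + 2 × 0.83 × 108 = 287.
- Surveys after the writing tasks: 2 × 0.83 × 108 = 179, up to 2 × 108 = 216.

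These count surveys, not high-risk answers. The documents give no rate from which to project the latter.

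**The case against.** The strongest reply is that the protocol is not silent on risk outside the writing. The imminent-risk rule and the commitment to act on clear intent apply whatever the source. Section VII recognises discomfort from self-report measures and trains staff to respond, including in less imminent cases. Anyone who completed a writing session already holds a local mental health contact before the two later surveys, so the lack of a resource page matters mainly at baseline and for participants who never wrote. The measures appendix and consent documents are not visible, and an alert or closing page could well be there.

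Most of this stands, and it rules out several stronger readings that a reader might infer:

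- That survey answers wait up to a quarter of a year. The quarterly review is at study level and sets no reading time for individual answers, short or long.
- That there is no trigger at all. What is missing is a survey-specific one.
- That a particular statement, such as a suicide plan, would be recorded on the SIDAS. The documents give the scale's name, not its items or scoring.
- That a given number of high-risk answers would be missed. No rate is stated.

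The reply does not supply a step by which anyone comes to see the survey answer, and every general provision depends on that step.

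A second objection concerns the remedy. Psychologist contact before the 3-month assessment is a co-intervention on depressive symptoms and suicidality. A trigger from the baseline survey precedes randomization and should be balanced in expectation. One from the post-intervention survey may differ by arm if an intervention works. That is a reason to record and report contacts by arm, not to leave answers unread.

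**Conclusion.** The concern holds for the visible text. The stated safety review covers 3 of 3 writing tasks and 0 of 3 surveys, although the surveys carry the direct suicidality and self-injury questions. This is more than missing detail, because the daily check can be followed to the letter with those answers unread. It is a cheap safety improvement that should be made; it does not affect the sample size or the validity of the planned model. The conclusion rests on one assumption, that the unseen appendix and consent pages contain no survey procedure. If they do, the remaining defect is a missing cross-reference. The range of 287 to 324 surveys assumes 108 enrolled and the retention cited in Section VIII; the gap itself depends on neither.

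**What to change.** If a survey procedure exists in the appendix, cite it where the writing review is described. If not, amend that text as follows:

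- Extend the daily check and the 24-hour limit to the suicidality, SIDAS and self-injury items in all three surveys, with a Qualtrics alert to the licensed psychologist at a threshold the investigators choose.
- Show the local mental health contact at the end of every survey.
- Use one trigger and one decision-maker for writing and surveys. At present the writing review has a research assistant call 911 on expressed intention, while Section V item 10 requires imminent risk judged by trained staff. Which to adopt is a clinical choice.
- Record each safety contact with its date and source, and report the counts by arm beside the 3-month results.

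The cost is a protocol amendment, an alert on a platform that is already checked daily, and some psychologist time. Participants who know that their answers are read may report less suicidality; the rule would be the same in every arm. Safety contacts before the 3-month outcome may dilute or distort the arm contrast, which is why they need reporting by arm. The sample size and the model stay as they are.

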#### 1. Recruitment Procedures:

a. Describe how potential participants will be identified and contacted, and by whom.

SECTION V: RECRUITMENT/CONSENT AND ASSENT PROCEDURES

We will recruit participants through postings and ads on geo-targeted websites (e.g., Craigslist, Facebook, Reddit), bulletin boards, and listservs at local colleges and universities (e.g., gay-straight alliance [GSA] listserv); mobile social networking apps (e.g., Grindr, Growlr, Instagram); and inperson announcement and flyers at local community centers, bars, community events, and through the GSAs of local area schools. Also, [name], at ETSU, maintains a "research repository" for people who sign up at community events to participate in future research studies. We will email the eligible LGBTQ+ individuals on this list with our study screener to determine their interest in participating in the present study. After completing the online screener, potential participants will be contacted by a trained research assistant (RA) who will explain the study purpose and procedures, verify eligibility, and review consent materials. Age eligibility will be verified by photo ID, requiring each participant to email a snapshot of themselves holding their photo ID. In our experience, an LGB sexual orientation identity is difficult to fake, especially in interviews such as ours that assess LGB cultural knowledge and contexts specific to LGB individuals.

The Phase 1 and Phase 2 LGB community leaders have already indicated their support for this project and we have their letters of support on file for the NIH funding application.

Are you collecting any inform Yes ⊠ No □	nation about the individuals prior to their signi	ng a consent form?
If yes, indicate what informati paper questionnaire, etc.)	ion you will be collecting and how it will be g	athered (phone screen,
assessed at the start of the scre call from study staff, who will	nts will complete an online screener through eener. Those determined eligible by the online explain to the potential participant the study ponsent. (See attached online screener text and	e screener will receive a purpose and procedures,
2. Indicate recruitment method used.	s below. Attach copies of any recruitment ma	nterials that will be
⊠ Flyers		Radio
⊠ Posters		Telephone
Letter	Departmental/Center Website	Television
Newspaper		
Through local NGO or other loc	eal contact Social Media (Facebook, Tr	witter)
Classroom recruitment		
Table set-up / in-person recruitm	ent of public	
Snowball sampling	-	
who sign up at community eve	[name], at ETSU, maintains a "research repents to participate in future research studies. V on this list with our study screener to determinedy.	Ve will email the
a. Targeted for enrolls	we the number of participants: ment at Yale for this protocol 0/not applicable study, give the total number of participants to 0 +108)	

## 4. How was this estimate derived?

15 LGB emerging adults (10 in Phase 1 and 5 in Phase 2) and 10 community leaders (10 in Phase 1, five of whom will repeat in Phase 2) is the estimated number of participants needed to develop and refine the intervention materials before saturation is reached, as per our previous similar intervention development research (e.g., [name] et al., 2013; [name], 2014).

Phase 3 of the project, which aims to recruit 108 participants (36 per each of three conditions: EW, SA, C), is powered primarily to examine feasibility and acceptability. This phase will allow us to determine the preliminary efficacy of the interventions. Our sample size provides sufficient power (1- $\beta$  = .8) to detect intervention effects consistent with effect size estimates identified in a meta-analysis of EW interventions across general population samples in which the average effect size (d) was .47 across physiological, psychological, self-reported health, and health behavioral outcomes. In order to detect an effect of .47 we need 36 participants per group. This sample size will also afford sufficient power (1- $\beta$  = .8) to detect moderation effects found in previous examinations of EW moderation (e.g., social support) (i.e., d = .46 $^{10}$ ), and estimate the direct path to and from the proposed mediators (stress and self-regulation), as secondary aims.

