NCT03751020

Title of Research Project: Development and preliminary trial of a
brief, portable health intervention for rural sexual minority
emerging adults

SAP Date 7.29.2019

Development and Preliminary Trial of a Brief, Portable Health Intervention for Rural Sexual Minority Emerging Adults

Statistical Analysis Plan

We will use hierarchical linear modeling to evaluate whether SA or EW demonstrate greater decreases from baseline in depressive symptoms, suicidality, substance use, and HIV risk behaviors, at post-intervention and 3-mo. follow-up relative to control participants. Level 1 will include time and the Level 2 variables will include intervention condition and possible covariates such as demographic and psychosocial variables. We will conduct “intent-to-treat” analyses in which all cases are analyzed and multiple imputation is used to estimate follow up data for treatment non-completers. Evidence for a significant main effect for improved outcomes will provide pilot data to justify a larger RCT examining the longer-term effectiveness (e.g., 6- and 12-month follow-ups) of one or both of our writing interventions. Analyses will also explore the degree to which social support, gender, baseline health risk, and identity centrality moderate intervention effects. Although we are likely not fully powered to detect mediation, our design and sample size allow us to estimate the size of the direct paths to and from the mediators—estimates that will determine the sample size for a future proposal. However, if the magnitude of the direct paths to and from the mediators are medium to large, as suggested by previous research, we would be sufficiently powered ($1 - \beta = .8$) to use a bias-corrected bootstrap approach to test mediation. Evidence for mediational effects will provide critical new information about mechanisms underlying SA and EW intervention efficacy.

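### The stated 80% power for d = .47 with 36 per group cannot be reproduced: its inputs are not given, and a plain two-arm comparison gives about 50%

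*Protocol*

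**What the plan says.** Protocol Section V, item 4 sets Phase 3 at 108 participants, 36 in each of EW, SA and control. It says the phase "is powered primarily to examine feasibility and acceptability". It then claims power of .8 "to detect intervention effects consistent with effect size estimates identified in a meta-analysis of EW interventions across general population samples", gives the average d in that meta-analysis as .47, and concludes: "In order to detect an effect of .47 we need 36 participants per group".

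The SAP describes the efficacy analysis: "We will use hierarchical linear modeling to evaluate whether SA or EW demonstrate greater decreases from baseline", "at post-intervention and 3-mo. follow-up relative to control participants". On the model it says only: "Level 1 will include time and the Level 2 variables will include intervention condition and possible covariates such as demographic and psychosocial variables". On missing data, "multiple imputation is used to estimate follow up data for treatment non-completers". On use of the result: "Evidence for a significant main effect for improved outcomes will provide pilot data to justify a larger RCT". It gives no sample-size inputs for this comparison.

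Three other places bear on the point. Section IV.1 (Aim 3) and Section IV.3 put the primary outcomes at 3 months. Section IV.2 (Specific Aim 3) gives the primary analyses the task of determining efficacy. Section VIII, item 2 reports 83–100% retention in the team's earlier longitudinal work but does not apply it to the sample size.

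**The concern.** A power statement can be checked only if it names the test. This one gives an effect size, a power and a group size, but no alpha, sidedness, contrast, time point, baseline correlation or dropout allowance. The SAP compares each writing intervention with control, and for an ordinary two-arm comparison 36 per group is about half of what d = .47 requires.

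What is at stake is how the result is read. The protocol and SAP use these analyses to judge efficacy and to decide whether a larger trial is justified. A reader who takes 80% at face value will treat a null result as stronger evidence against EW or SA than it may be, and a promising arm could be dropped for that reason.

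**Working it through.** **Inputs from the documents.** d = .47, target power .80 and 36 per group (Section V, item 4). Comparison with control at post-intervention and 3 months (SAP). Retention of 83–100% in earlier work (Section VIII, item 2); 0.83 × 36 = 29.9, taken as 30 per arm.

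**Assumed, because not stated.** Alpha .05, two-sided unless noted. No multiplicity adjustment. Continuous outcomes analysed on a normal scale, with d in single-visit SD units. Baseline correlation r varied over .5, .6 and .7.

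**Step 1: plain two-arm comparison.** Noncentral t with noncentrality d × √(n/2) and df = 2n − 2. For n = 36 this is .47 × √18 = 1.99.
- Power is .503 with 36 per arm and .433 with 30 per arm.
- Required n: 72 per arm gives .7998 and 73 gives .805.
- The detectable d at 80% power with 36 per arm is .67.

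**Step 2: other simple readings, 36 per arm.**
- One-sided .05, one active arm against control: .629.
- Both active arms pooled against control (72 v 36): .626 two-sided, .740 one-sided.
- Three-group ANOVA with both active arms differing from control by d: .516.

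None gives .80.

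**Step 3: where 36 does appear.** The normal approximation for a single-group pre/post test is (1.960 + .842)² / .47² = 35.5, which rounds up to 36. The exact t version needs 38. Comparing two arms doubles the approximation to 71.1 per arm. The documents do not say how 36 was obtained, so this is a numerical match and not an explanation.

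**Step 4: allowing for baseline and repeated measures.** The SAP does not say whether baseline enters as an outcome (contrast of change) or as a covariate, so both are shown. The effect d is divided by the square root of a variance factor:
- change at 3 months: 2(1 − r)
- baseline-adjusted at 3 months: 1 − r²
- mean of two follow-ups, equal correlations: 1.5(1 − r) for change, (1 + r)/2 − r² adjusted

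The df are 2n − 2 for change and 2n − 3 for adjusted.

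| Two-sided, one active arm v control | r = .5 | r = .6 | r = .7 | r for 80% |
|---|---|---|---|---|
| Change at 3 months, 36/arm | 50% | 59% | 72% | .75 |
| Adjusted at 3 months, 36/arm | 62% | 69% | 79% | .71 |
| Change at 3 months, 30/arm | 43% | 52% | 64% | .80 |
| Adjusted at 3 months, 30/arm | 54% | 61% | 71% | .77 |
| Change, mean of both follow-ups, 36/arm | 62% | 72% | 83% | .67 |
| Adjusted, mean of both follow-ups, 36/arm | 79% | 84% | 91% | .51 |

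The 30-per-arm rows let dropouts contribute nothing. If 6 of 36 per arm miss only the 3-month visit and their earlier data are used (generalised least squares, equal correlations), 3-month power is 45/54/66% for change and 55/62/72% adjusted.

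**Step 5: the most favourable readings.** At 3 months with 36 per arm, the correlation needed for 80% falls to .68 (change) or .61 (adjusted) one-sided, and to .67 or .58 for pooled arms two-sided. With both follow-ups averaged and baseline adjusted, power at r = .5 is 87% one-sided or 90% pooled two-sided.

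**The case against.** The strongest reply is that 50% does not describe the planned analysis. The SAP specifies a hierarchical model using baseline and two follow-ups and looks for a main effect. The baseline-adjusted mean of both follow-ups gives 79% to 91% for r = .5 to .7. On that view the fault is missing inputs, and no miscalculation has been shown. Much of this stands: the calculations do not show that the trial is underpowered, and 80% is attainable under some readings. It does not rescue the sentence as written, because no correlation, contrast or averaging is stated. The protocol also places the primary outcomes at 3 months, where r = .5 to .7 gives 50% to 79% for a two-sided pairwise test.

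A second reply is that this is a pilot, sized mainly for feasibility and acceptability. That limits the consequence and is a good reason to leave N alone. The same paragraph nevertheless asserts power of .8 for efficacy.

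Three smaller points are fair. The match with a single-group formula is only approximate and proves nothing about the source of 36. The illustrative percentages assume continuous normal outcomes, which may not suit suicidality, substance use or HIV risk behaviour. Letting dropouts contribute nothing differs from the SAP's multiple imputation, although the partial-data version differs by only about 1 to 2 percentage points.

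**Conclusion.** The concern holds. The claim that 36 per group are needed for, and give 80% power at, d = .47 is not reproducible from the documents. It is wrong for a plain two-arm comparison at two-sided .05, where power is about 50% and 72 to 73 per arm are needed. It can be true only with assumptions that are not stated: for a two-sided pairwise test, a baseline correlation of about .71 to .75 at 3 months, or about .51 to .67 if both follow-ups are averaged. A one-sided or pooled contrast needs less.

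Confidence is high that the inputs are missing and that the simple calculations do not give .80. The true power of the planned model cannot be fixed without those inputs. This should be corrected, but it is a correction of a stated figure and does not call for a larger sample.

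**What to change.** Keep N = 108. If the team still has the calculation behind 36, state it in Section V, item 4: alpha, sidedness, contrast, time point, model, correlation with its source, attrition and resulting power. That alone would resolve the point.

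Otherwise, remove the statement that 36 per group are required for d = .47 and replace it with wording such as:

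> For each active arm against control at 3 months, with two-sided alpha .05 and d in single-visit SD units, 36 per arm gives about 50% power for d = .47 without gain from baseline (detectable d about .67). For baseline/3-month correlations of .5, .6 and .7, power is 50%, 59% and 72% if the model contrasts change from baseline, and 62%, 69% and 79% if baseline is adjusted for. With 30 per arm (83% retention, dropouts contributing nothing), power is 43% without baseline gain; 43%, 52% and 64% for change; and 54%, 61% and 71% adjusted.

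If the intended test averages both follow-ups, is one-sided or pools the active arms, say so and give the matching figure. The next sentence in that item claims the same power for moderation at d = .46, also without inputs, and should be given its inputs in the same edit.

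The cost is protocol wording only. The downside is a less favourable stated power unless the missing inputs can be supplied.
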